Aim 2: Does a multilevel intervention work better? We will assess the effects of combining a brief intervention and SSB sales ban on outcomes. We will compare outcomes for participants exposed to the multilevel intervention ($n=175$) to those who receive the: (a) brief intervention only ($n=175$), (b)

**SUTTER HEALTH
INSTITUTIONAL REVIEW BOARD**

Protocol Summary Form

sales ban only ($n=175$), and (c) no intervention ($n=175$). *We hypothesize that the combined intervention will have a greater effect on outcomes than the brief intervention or sales ban alone. Higher-risk employees (see Aim 1) will benefit more from the multilevel intervention than their lower-risk counterparts.*

Aim 3: (Exploratory): How does the intervention work? We will test whether changes in SSB cravings mediate the effects of the multilevel intervention on outcomes. The multilevel intervention seeks to increase motivation to reduce SSB intake while reducing environmental cues to drink SSBs. *We hypothesize that the multilevel intervention will lead to the greatest reductions in cravings for SSBs, and cravings will mediate its effects on outcomes. We will explore mediation across high-risk groups (see Aim 1).*

2. BACKGROUND:

Obesity and type 2 diabetes are pressing health concerns, particularly for lower-income and ethnic minority employees. Obesity rates are at an all-time high and disparities persist: 49.6% of adult African Americans are currently obese and 44.8% of Latinos, compared to 42.2% of non-Hispanic whites.¹³ Diabetes rates have nearly doubled since 2000.¹⁴ Employers face disproportionately rising obesity-related healthcare costs alongside productivity losses.¹⁵ Obesity is major concern for occupational safety, particularly for physically active nurses, manual workers and technicians at heightened risk for injury.^{15,16}

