Waist Circumference	A tape measure with instructions will be provided to the participant to measure at the designated timepoints.	X	X	X
Fasting Blood Draw	The collection will include: complete metabolic and lipid panel, uric acid, ApoB, GGT, glucose, insulin, HbA1c. These are biomarkers that are risk factors for poor metabolic health, diabetes, and cardiovascular disease	X		X
BevQ	This questionnaire seeks to quantify the frequency, type and volume of beverages consumed at work and home.	X	X	X

**SUTTER HEALTH
INSTITUTIONAL REVIEW BOARD**

Protocol Summary Form

ASA 24	This is a web-based, 24-hour dietary recall tool developed by the National Cancer Institute	X	X	X
Stanford Leisure Time Scale (L-CAT)	This is a scale that measures physical activity.	X	X	X
*PROMIS4a Depression	Assesses the presence and severity of symptoms of depression.	X	X	X
Beverage Craving Questionnaire (FCQ-T-R)	Assesses the following: 1) preoccupation with sweetened beverages; 2) loss of control; 3) positive outcome expectancy; 4) emotional cravings	X		
Reward Based Eating Drive (RED-13)	Assesses three aspects of drive to eat: 1) loss of control; 2) lack of satiety; 3) preoccupation with food	X	X	X
Perceived Stress Scale	This is a widely used questionnaire to assess stress levels. It evaluates the degree to which an individual has perceived life as unpredictable, uncontrollable, and overloading over the previous month.	X	X	X
Copenhagen Burnout Inventory (CBI)	This six-item inventory measures personal burnout experienced by participants.	x	x	x
Self-Efficacy	These questions are used to determine if an individual exhibits intention to reduce SSB consumption.	X	X	X
Science of Behavior Change Texts Parent Grant	Assesses craving, psychological stress, consumption and self-efficacy (two texts/day x four days/week)	X	X	X
Science of Behavior Change Texts Supplemental Grant	Assesses craving, psychological stress, consumption and self-efficacy (two texts/day x four days/week)	Additional texts will be sent at the following time periods: 1, 2, and 3 months after SSB intervention.		
EPIC EMR	Lab results from the blood draw will be extracted from EPIC utilizing the resources of the Center for Health Services Research (CHSR). Limited data from the medical record will be extracted by CHSR that looks at metabolic health.	X		X
Incentive Gift		X	X	X

**SUTTER HEALTH
INSTITUTIONAL REVIEW BOARD**

Protocol Summary Form

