The Automated Self-Administered 24-hour Dietary Assessment Tool (ASA24): The ASA24 is a free, web-based tool that enables multiple, automatically coded, self-administered 24-hour diet recalls and/or single or multi-day food records. ASA24 was developed by the National Cancer Institutes. Participants will be asked to complete one 24-hour recall at enrollment, 6 and 12 months using a link and password sent to them.

The Stanford Leisure-Time Categorical Item (L-CAT): The L-CAT is a questionnaire asking participants to rank their activity level from inactive to very active. This tool has been validated and can detect statistical differences when used over time.

Patient-Reported Outcomes Measurement Information System (PROMIS) Depression: The PROMIS Depression 4-item questionnaire banks assess self-reported negative mood (sadness, guilt), views of self (self-criticism, worthlessness), and social cognition (loneliness, interpersonal alienation), as well as decreased positive affect and engagement (loss of interest, meaning, and purpose). The depression short forms are universal rather than disease specific. All assess depression over the past seven days. If they score in the severe range the Clinical Research Coordinators will contact the participant and will provide them with the EAP contact information and will encourage them to call EAP.

Food Craving Questionnaire-Trait, Reduced (FCQ-T-r): The 15-item FCQ-T-R assesses (1) preoccupation with SSB (i.e., obsessive thought about food and eating), (2) loss of control (i.e.,

**SUTTER HEALTH
INSTITUTIONAL REVIEW BOARD**

Protocol Summary Form

difficulty regulating eating behavior when exposed to food cues), (3) positive outcome expectancy (i.e., believing eating to be positively reinforcing), and (4) emotional craving (i.e., tending to crave food when experiencing negative emotion).

Reward Based Eating Drive (Red-13): The 13-item RED assesses three aspects of drive to eat (loss of control, lack of satiety, and preoccupation with food). Items are answered on a Likert scale from 0 (Strongly Disagree) to 5 (Strongly Agree). Example items include "I feel out of control in the presence of delicious food" and "When I start eating, I just can't seem to stop."

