Using the Ecological Momentary Assessment (EMA) approach, cravings will be measured by study participants using smart phones. Using the REDCap platform, participants will receive a short set of questions at the following timepoints: baseline, 1, 2, and 3 months after SSB intervention starts at randomized affiliates, and 6 and 12-months. Two texts will be sent each day (morning and evening) four of the seven days of the week. Participants will be asked to quickly record the following: cravings (if any) for sugar sweetened beverages, psychological stress, consumption, and psychological stress. The primary target for this exploratory analysis is cravings for SSBs but we will also have access to information on whether or not subjects consumed SSBs in response to the craving. Each text should take one to-five minutes each. The content of the text is as follows:

- Introductory text at the start of each assessment period (Sunday afternoon) shall read:
 - o *Greetings Sweet Study Participant – this week, we’ll text you 4 clickable links in the morning and 4 in the evening on Tues, Thurs, Fri, and Sat. Each link will take 1-5 minutes to complete – Short and Sweet! The week after you finish the surveys, we’ll email you a \$10 gift code. Please complete at least 6 of the 8 texts in order to receive a gift code.*

Each day, the texts will be labeled as morning Sweet text 1, 2, 3, 4 and evening Sweet text 1, 2, 3, 4.

Location (asked in evening)

Today, were you physically working at your Sutter Health workplace?

**SUTTER HEALTH
INSTITUTIONAL REVIEW BOARD**

Protocol Summary Form

- Yes
- No

Can define a sugary drink here.

Craving Battery – Evening – Supplement and Parent

1. Today, did you crave a sugary drink? Yes / No

- If No, skip #2 and #3
- If Yes: Move on to #2.

2. At its most severe point, how strong was your craving for a sugary drink today?

Sliding bar, slider starting at middle or optimally nowhere and it gets placed when the respondent touches the screen, if starting in the middle then movement of bar required to advance to next question

**For #3, make these checkboxes, with the first two non-exclusive, and the “no” exclusive*

3. Did you drink anything in response to ANY of these cravings?

- Yes, a sugary drink
- Yes, water, a sugar-free drink, or a drink with no added sugar
- No

Psychological Stress Battery - Evening – Supplement and Parent

What was your overall mood like during the day?

1. I felt stressed, anxious, overwhelmed.

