Analysis Plan for Aim 3: (Exploratory): *How does the intervention work?* We will test whether changes in SSB craving mediate the effects of the multilevel intervention on outcomes.

Introduction: The goal of this analysis is to examine SSB craving as a mediator in the relationship between the multilevel intervention and primary and secondary health outcomes. This is justified by our pilot study analysis showing that employees with a high level of baseline craving benefited more from the multilevel intervention than comparable employees exposed to the sales ban alone.¹² This study is designed to test the mediation model for the sales ban and brief intervention separately, helping us to understand the “active ingredients” in the multilevel intervention. We can also explore differential benefits for members of high-risk groups.

Research Design for Aim 3: This exploratory analysis will estimate mixed effects using logistic regression models. In contrast to some approaches toward mediation analysis (e.g.,¹¹¹⁻¹¹⁴), ours will

**SUTTER HEALTH
INSTITUTIONAL REVIEW BOARD**

Protocol Summary Form

simultaneously test all paths, including indirect effects through the mediator,¹¹²⁻¹¹⁴ regardless of the presence of a statistically significant total intervention effect.¹¹⁴ Available measures allow us to examine the extent that changes in SSB cravings and SSB consumption after cravings mediate the effects of the multilevel intervention on outcomes.

Key Measures for Aim 3: In addition to measures described above, this aim incorporates text message-based EMA data that captures SSB cravings in the context of day-to-day life.

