Analytic Plan for Aim 3: Participants will respond to a question asking if they experienced a craving for SSBs as *yes* or *no*. We will use this SSB craving variable (M), along with group assignment (X), to predict 12-month SSB consumption (Y). This simultaneous mediation model will comprise, first, a mixed effects logistic regression model (Path A in Figure 2 above, from X to M). This model will include random effects for day nested within study period, nested within person for each of the possible reports per day (morning, afternoon, evening, and “any other time not previously reported”). The dependent variable will be the dichotomous primary outcomes reflecting the experience of a craving or whether a craving was acted upon. Model covariates (fixed effects) include time of day, study period, randomization group, and the interaction of study period by randomization group. This will allow us to estimate the odds of having a craving or indulging in one at 6- and 12-months compared to baseline, separately for each experimental arm, as well as allowing for direct comparisons between study arms at each time point.

A second component of the model is a mixed effects linear regression model (Path B in Figure 2 above, from M to Y) that links a change in cravings between baseline and the 6-month follow up (measured as the change in the proportion of responses in which subjects reported cravings) to SSB consumption and HOMA at 12 months. We will perform this mediation model first without covariates¹¹⁵ and then will perform it with other predictors of SSB consumption (e.g., demographics, high-risk group) as in Aim 1. This analysis will allow us to estimate the proportions of variance in SSB consumption at 12 months that are related to changes in SSB craving experiences.

The relationship between the interventions and SSB consumption without the inclusion of craving (Path C) will have already been established in the analyses for Aims 1 and 2, so lastly, we will examine Path C' (interventions predicting consumption and waist change with the inclusion of the craving mediator). This will necessitate a model similar to those used in Aims 1 and 2, but with the addition of craving change and an interaction term for intervention*craving change.

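### Craving change is the Aim 3 mediator, but the 15-item craving scale is given at baseline only and the Path B change score rests, as the text battery is printed, on at most four yes/no reports per wave

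*Combined protocol and SAP*

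**What the plan says.** Aim 3 in section 1 states: "We will test whether changes in SSB cravings mediate the effects of the multilevel intervention on outcomes".

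The schedule in section 4b lists one multi-item instrument for beverage craving, in the row that begins "Beverage Craving Questionnaire (FCQ-T-R". It is marked at baseline, and its 6- and 12-month cells are blank. The other questionnaires in that table (BevQ, ASA24, L-CAT, PROMIS depression, RED-13, Perceived Stress Scale, Copenhagen Burnout Inventory, self-efficacy) are marked at all three time points. The instrument description under the table reads "The 15-item FCQ-T-R assesses (1) preoccupation with SSB" and goes on to three further domains. It does not say why the scale is not repeated.

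The mediator data come from text messages. Under Key Measures for Aim 3, "this aim incorporates text message-based EMA data that captures SSB cravings in the context of day-to-day life". The Analytic Plan for Aim 3 makes the variable binary: "Participants will respond to a question asking if they experienced a craving for SSBs as" yes or no. Path B "links a change in cravings between baseline and the 6-month follow up", with that change "measured as the change in the proportion of responses in which subjects reported cravings". The outcomes are SSB consumption and HOMA at 12 months.

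On text frequency, section 4b says: "Two texts will be sent each day (morning and evening) four of the seven days of the week". The craving battery is labelled as an evening battery, and the only battery labelled for the morning is self-efficacy. The Aim 3 analytic plan, however, describes morning, afternoon, evening and other-time reports.

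**The concern.** The scale that addresses the proposed mechanism most directly is the only questionnaire in the schedule that is not repeated, and no reason is given. Path B then depends on a difference between two proportions, each of which may have a denominator of four or fewer.

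Random error in a mediator pulls the mediator-to-outcome slope toward zero. It also moves the direct effect (Path C') toward the total effect, because the adjustment for craving change is incomplete. The likely mistake therefore runs one way: concluding that craving does not explain an intervention effect when it partly does. Section 3 says that Aim 3 will show why the intervention worked or guide later ones, so a false negative here would mislead. The Aim 3 text on anticipated problems does not expect trouble in detecting small mediation effects, but it does not discuss error in the change score.

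**Working it through.** **1. Is the blank in the schedule real?** Probably. The neighbouring rows keep their three marks. The fasting blood draw row keeps its blank 6-month cell, and the text of section 4b confirms that labs are drawn only at baseline and 12 months. The table layout therefore appears to have survived extraction.

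**2. Reports per wave.** Aim 3 has no power or sample-size figure to reproduce. The plan's own count is 8 texts per wave: 2 per day × 4 days = 8, which agrees.
- Craving asked in the evening only: 1 × 4 = 4 reports.
- The gift code requires 6 of 8 texts. Four mornings plus two evenings meets it, so a participant who earns it may supply only 6 − 4 = 2 craving reports.
- If the four report times in the Aim 3 analytic plan were collected: 4 × 4 = 16 reports.

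**3. Coarseness and sampling error for one person.** With four reports a wave proportion takes 5 values and the change score 9. The standard error is √(p(1−p)/k) per wave, multiplied by √2 for the change. This treats reports as independent given the person's true rate, with the same p at both waves.

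| Reports k | p | SE, one wave | SE, change |
|---|---|---|---|
| 2 | 0.5 | 0.35 | 0.50 |
| 4 | 0.5 | 0.25 | 0.35 |
| 4 | 0.3 | 0.23 | 0.32 |
| 16 | 0.5 | 0.125 | 0.18 |

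**4. Reliability of the change score.** The documents give no variance inputs, so two sets of assumptions are used.

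*(a) Intraclass correlation (ICC) route.* Wave reliability is r = k·ICC/(1 + (k−1)·ICC). Change reliability is r(1−ρ)/(1−rρ), where ρ is the true between-wave correlation. Assumed: ICC 0.1 to 0.5, ρ 0.5 or 0.7. Worked case for k = 4, ICC 0.2, ρ 0.5: r = 0.8/1.6 = 0.50, and change reliability = 0.25/0.75 = 0.33.

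| ICC (k = 4) | Wave reliability | Change, ρ = 0.5 | Change, ρ = 0.7 |
|---|---|---|---|
| 0.1 | 0.31 | 0.18 | 0.12 |
| 0.2 | 0.50 | 0.33 | 0.23 |
| 0.3 | 0.63 | 0.46 | 0.34 |
| 0.5 | 0.80 | 0.67 | 0.55 |

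With k = 16 the same grid gives 0.35 to 0.89.

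*(b) Simulation route.* Each person has a log-odds of craving (SD 1.0 to 1.5) and a true change in log-odds (SD 0.5, 1.0 or 1.5), with binomial reports at each wave. Reliability is var(true change)/var(observed change).

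| SD of true change | k = 2 | k = 4 | k = 16 |
|---|---|---|---|
| 0.5 | 0.05 | 0.09 | 0.28–0.29 |
| 1.0 | 0.15–0.16 | 0.26–0.27 | 0.59–0.60 |
| 1.5 | 0.26 | 0.42 | 0.74 |

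The SD of true change drives the result. The person-level SD and the mean craving rate hardly alter it.

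**5. Effect on Path B.** With a single error-prone predictor, the expected slope is reliability × true slope. At 0.67 the loss is 1 − 0.67 = 33%. At about 0.1 it is about 90%.

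**The case against.** The plan never names the FCQ-T-R as the mediator. It chooses repeated text assessment for change, and the scale is by name a trait questionnaire. The pilot also used baseline craving to separate stronger from weaker cravers. A trait scale at baseline with texts for change is a coherent design, although the documents do not state that rationale. This stands, and it is why the point is an improvement and not an error in the plan.

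A reader might infer that yes/no evening reports are the only craving data after baseline. They are not. The evening battery also has a craving-strength slider, shown after a yes, and an item on what was drunk in response. The Aim 3 plan uses whether a craving was acted upon as a further outcome. Texts also go out at 1, 2 and 3 months. The restriction applies to the Path B change score, which as written uses neither the slider nor those waves.

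The cap of four is also not beyond dispute, because the Aim 3 analytic plan names more report times than the battery collects. If 16 reports per wave were really planned, the problem would be much smaller.

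Finally, the documents do not show that the scale responds to change over 6 months, and a second mediator adds a test to a plan with no formal control of multiplicity. Both are fair limits on the benefit. RED-13 is repeated but concerns drive to eat food, so it does not fill the gap.

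**Conclusion.** The point holds for Path B. As the battery is printed, the mediator change score rests on at most four yes/no reports per wave, and no multi-item craving score exists after baseline. Reliability is roughly 0.1 to 0.67 with four reports, which means a loss of about one third to 90% of the Path B slope. With 16 reports the simulation gives about 0.3 to 0.74. These ranges rest wholly on assumed variances.

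It would be tempting to quote only the simulation and report a loss of 58% (1 − 0.42) to about 90% as settled. The documents do not support that precision, because equally plausible ICC assumptions bring the loss down to about 33%. A reader might also infer that the whole mediation analysis, or the trial's main result, is compromised. It is not. Path A is a mixed logistic model on individual reports, so this calculation does not describe it, and the primary outcomes do not use craving. Aim 3 is labelled exploratory. This is a low-priority, inexpensive improvement, but 6-month scale scores that are not collected cannot be recovered later.

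**What to change.** 1. Mark the FCQ-T-r at 6 and 12 months in the section 4b schedule and add it to the REDCap questionnaires already sent then. Name its baseline-to-6-month change as a supplementary exploratory mediator alongside the text measure, not in place of it.
2. Reconcile the text battery in section 4b with the report times named in the Analytic Plan for Aim 3, and state the maximum number of craving reports per wave.
3. Pre-specify use of the craving-strength slider, including how a day with no craving is scored, and of the 1-, 2- and 3-month waves. As an illustration, pooling those waves with 6 months gives up to 4 × 4 = 16 follow-up reports. At p = 0.5, if the follow-up rate is stable, the SE of the change falls from 0.35 to √(0.25² + 0.125²) = 0.28. The four baseline reports then limit further gain. Pooling also changes the quantity to an average over follow-up, which the plan should say.

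Cost: two schedule marks and 15 items at two time points, a few minutes each, with no visits or staff. The downsides are slightly more participant burden, one more exploratory test, and unproven sensitivity of a trait scale to 6-month change. Items 2 and 3 add no burden if the battery stays as printed.

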Public health impact: If effective, the proposed employer-sponsored multilevel intervention will offer an efficient, scalable strategy for preventing obesity in millions of American working adults. This study will also contribute to science on mechanisms of change in obesity prevention and inform the design of interventions that exploit synergies between individual behavior change strategies and food environment policies.

4. METHODS:

(4a) General Study Design:

This is a prospective, double-randomized study in which 16-Sutter Health affiliate hospital campuses will be cluster randomized to control (no SSB sales ban) vs. intervention (removal of SSBs). Across these 16 campuses, we will enroll 700 employees and then randomize those who self-report consuming >30 oz of SSB per week to receive a brief counseling intervention or control (no intervention).

**SUTTER HEALTH
INSTITUTIONAL REVIEW BOARD**

Protocol Summary Form

(4b) Procedures:

Cluster Randomization of 16 Sutter Health Affiliates

Sutter Health affiliates will be eligible to participate in the study who meet the criteria: 1) the affiliate has not participated in a SSB intervention; 2) the affiliate is not in a county that has instituted a SSB sales tax. Affiliates will be stratified by their location (urban vs. rural) and number of employees and will be randomly assigned using a computer program to be assigned to either control or intervention. Sutter Health leadership ([name] and [name]) have signed a letter of support to conduct this study.

Sites randomized to the SSB will eliminate sugar-sweetened beverages from the cafeterias, vending machines, Walgreens, vendors, and from patient care areas. Sutter Health has already implemented Healthy Beverage Initiatives (HBI) at Alta Bates, Palo Alto Medical Foundation (PAMF) and all CPMC campuses.

Study Procedure	Description	Baseline	6 Months	12 Months
Informed Consent	Procedures Described Below	X		
Demographics	Self-reported gender, ethnicity, household income, education, work location, hours, shifts	X	X	X
Medical History	Self-reported concurrent medications and general medical history with an emphasis on diabetes	X	X	X
Height	Measured using a stadiometer on a standardized scale at a semi-private location on the affiliate campus.	X		
Weight	Obtained on a standardized scale at a semi-private location on the affiliate campus.	X	X	X

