***Patient-Reported Outcomes Measurement Information System (PROMIS):** We have selected a self-report measures of depression which are person-centered which all study participants will be asked to complete. We will investigate the possible correlation between SSB consumption, general health and depression as well as change over time between the intervention and control campuses. Subjects who report high levels of depression will be provided with contact information to Sutter Health's Employee Assistance Program (EAP). No documentation will be placed in the subject's medical or employment record.

REDCap will be set-up with a notification alerting the CRCs when the depression scores result with severe depression. When the participant completes their questionnaires, the Clinical Research Coordinators will review the depression questionnaire. If a participant scores a severe depression (score, a phone call will be made to the participant using a script. A form has been created and will be used as documentation. This includes a script for leaving a message and for a live call. During a live call only, the Clinical Research Coordinator will inform the participant of their high score and will with the phone number to Sutter Health's EAP.

Demographics: Including gender, ethnicity, primary work location, occupational status, income, and usual number of worked shifts each week will be recorded via REDCap.

Medical History: Concurrent medications and general medical history will be obtained directly from study participants with an emphasis on metabolic history such as diabetes. Data will be recorded via REDCap

Height, weight, and waist circumference measurements: Subjects will be asked to record their self-reported height in REDCap. Height and weight will be measured using a standard scale with an attached stadiometer in a semi-private location at the affiliate and record their weight and height in REDCap. A tape measure and instructions on measuring waist will be sent to the participant's home. They will record the measurement in REDCap.

Fasting Blood Draw: A fasting blood draw will take place at the draw station of the local affiliate. Labs will be drawn at baseline and at 12-months. The panels will be comprised of metabolic and lipid panels that pertain to metabolic syndrome. Labs will be accessible to participants using My Health Online.

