Medical Record: Medical record data will be requested for the Sutter EHR (Epic) over a seven-year period (to include one year prior to enrollment, the 12-month study period and for five years thereafter). Data collection will include metabolic parameters related to obesity, such as: lipid panels, glucose, insulin, liver panels, height, weight, and past and prospective history. Medical records data collection will include medication history, progress reports, discharge summaries, and other data allowing us to look at the long-term impact of metabolic health in this population.

Depression: We will investigate the possible correlation between SSB consumption, general health and depression as well as change over time between the intervention and control campuses.

**SUTTER HEALTH
INSTITUTIONAL REVIEW BOARD**

Protocol Summary Form

Benefits: In cooperation with SutterSelect, we will obtain aggregate claim information for subjects at the intervention and control campuses. The aim of this data is to evaluate differences in health plan costs between the two groups. No individual health claims information will be collected. The data access form will review the security and privacy controls to ensure protections are in place. This data will be collected one year prior to enrollment, the 12-month study period and five years after.

Questionnaires: Subjects will complete all questionnaires remotely using a secure instance of REDCap.

BEVQ: BEVQ is a food frequency questionnaire measuring specific beverage items. We will use an adapted version of the BEV-Q field tested in the UCSF studies that captures beverage consumption while in the workplace and while not at work. The questions ask the type and frequency of consuming specific types of beverages on a typical day: regular/non-diet soda, diet soda, 100% fruit juice, fruit drinks (lemonade, smoothies), sports or energy drinks, sweetened coffee or tea drinks (Arizona iced tea, Frappucinos), and water. Participants also report how much (in ounces) they consume of each beverage each time over a limited, one week, recall period. Daily intake can be calculated for each beverage type by multiplying the frequency and serving size

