Copenhagen Burnout Inventory (CBI): The 6-item portion of the CBI assess personal burnout as is a state of prolonged physical and psychological exhaustion. Participants quantify the frequency of physical and emotional fatigue, as well as their susceptibility to illness, from on a six-point scale from "Always" to "Never". Formulated in a way that all human beings can answer it (regardless of job status), the measure was validated through the PUMA study.

Participant Randomization

Upon completion of five enrollment measurements (questionnaires, height/weight, waist, ASA24, and blood draw) participants will be randomly assigned to either a control group, or a group receiving a brief, remote motivational intervention, known as the Metabolic Health Improvement Plan (MHIP). Participants are randomized by a REDCap randomization module, using stratified random sampling by location. Those randomized to intervention will be contacted as described below.

SSB Brief Motivational Counseling Intervention- The Health Improvement Program

Participants randomly assigned to the health improvement program and will be contacted to participate in an education session with a trained coach via phone or video conference. The session led by a trained coach will describe the amount of sugar ingested in SSBs per week and will then proceed to provide personal guidance on health risks and the benefits of reducing sugar intake. Next, the coach will engage the participant in achievable, gradual goals to reduce SSB consumption reviewing and providing education materials. This will include discussing substitution beverages and preferred alternatives. Coaches will provide tools to the participant to increase self-efficacy and mediate the impact of stress, and cravings. The brief counseling session ends with the coach providing education materials including recordings relevant to the discussion, which can include topics of stress reduction and mindfulness. Depending on the participant, the brief intervention will take between 15 and 25 minutes to complete.

The coach will make two, 5-minute booster telephone calls within 4-6 weeks of the initial call. The first will be about two weeks after the initial session and the second call will be about two weeks later. The coach will revisit goals and obstacles and determine compliance to the educational materials.

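### The plan promises EAP contact details after a severe depression score, but the only delivery step it describes is a phone call that appears to give the number only if answered live

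*Combined protocol and SAP*

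**What the plan says.** All of this is in section (4b), Procedures.

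- **Schedule table.** The PROMIS depression row ("Assesses the presence and severity of symptoms of depression") is marked at baseline, 6 months and 12 months.
- **Questionnaires paragraph.** "Subjects will complete all questionnaires remotely using a secure instance of REDCap".
- **PROMIS footnote to the table.** "Subjects who report high levels of depression will be provided with contact information" for the employer's EAP. It adds that nothing goes into the medical or employment record.
- **REDCap alert paragraph, directly after the footnote.** A severe score alerts the coordinators, who review the questionnaire and telephone the participant from a script. A form has been prepared: "This includes a script for leaving a message and for a live call". The next sentence reads: "During a live call only, the Clinical Research Coordinator will inform the participant of their high score and will with the phone number", and goes on to name the EAP.
- **Description of the PROMIS Depression instrument.** "If they score in the severe range the Clinical Research Coordinators will contact the participant and will provide them with the EAP contact information". Coordinators are also to urge the participant to ring the EAP.

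**The concern.** The promise and the procedure do not have the same reach. The footnote and the instrument description promise the EAP details without any condition on how the participant is contacted. The alert paragraph, the only place that says how this happens, appears to limit the number to calls that are answered. It also foresees that some calls will end in a message.

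A coordinator following that paragraph literally would leave a message without the EAP number. If that participant is never reached live, the promise is not kept. Handing over the EAP details is the plan's one stated protective action after a severe score. The questionnaire is completed remotely, so no staff member is described as present when the score is entered. What is at stake is participant safety; no estimate or test in the trial depends on it.

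**Working it through.** No arithmetic applies: the plan gives no figure here, and the documents give no inputs for one. The check is a reading of every place where the EAP, the depression score or a channel to participants is mentioned.

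**1. Is the promise conditional?** No. The footnote is triggered by high levels of depression, the instrument description by a score in the severe range. Neither mentions a live call.

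**2. What delivery is described?** One sequence: REDCap alert, coordinator review, scripted phone call. The instrument description speaks of contacting the participant but names no second channel.

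**3. What does the live-call condition cover?** It opens a sentence with two coordinated actions: telling the participant the score, and an action with the EAP phone number whose verb is lost. There are two readings.

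| Reading | Score given | EAP number given | Participant reached only by message |
|---|---|---|---|
| A (natural): condition covers both actions | Live call only | Live call only | Does not get the number |
| B (possible): condition covers the score alone | Live call only | Not restricted | Gets it only if the unseen message script includes it |

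Reading A is the more natural because the condition comes before both actions and directly follows the mention of a separate message script. Under B the plan still does not state that the message carries the number.

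**4. Is there a fallback elsewhere?**

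- Section 5, Risks/Discomforts, covers the blood draw and confidentiality. It mentions neither depression nor the EAP.
- Part IV, Other Comments, adds nothing.
- Weight is taken at all three waves ("Obtained on a standardized scale at a semi-private location on the affiliate campus"), but no handover of EAP details is described there.
- An email address is collected for electronic consent (Part II, section 2C), and email outreach is planned for retention (section (4c), Aim 1, Anticipated Problems). Neither is linked to the EAP.
- Out-of-range blood results are handled differently: the Blood Draw paragraph in (4b) sends results through My Health Online and asks participants to review them with their primary care physician. Nothing similar is described for the depression score.

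**5. Count from the text.** PROMIS waves: 3. Described delivery routes: 1. Described routes for a participant never reached live: 0.

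**The case against.** The strongest reply is that the gap is inferred from a damaged sentence and from papers that cannot be seen.

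- **The sentence lacks a verb, possibly through text extraction.** This is fair, and the damage is not counted as an error. The condition and its object are intact, so the natural reading survives, but reading B cannot be excluded.
- **Unanswered calls were foreseen.** A message script exists and may give the number or ask for a call back. This stands. The documents support saying that no other route is described; they do not show that unreached participants never get the number. A call back would become a live call, so the gap is confined to participants never reached live.
- **Consent pages are not available and might list support contacts.** This also stands as a limit: the count of zero applies to the visible text.
- **The instrument description leaves the duty open.** It says contact, not call, so email is not excluded and a message alone does not discharge the duty. That is correct, but it does not tell a coordinator what to do when the phone fails, and it sits beside a sentence that appears to withhold the number from messages.
- **The live-call rule protects privacy.** Participants are employees of the health system running the study, and keeping a depression score out of voicemail is sensible. That is a reason to restrict disclosure of the score. General EAP details shown to everyone would disclose nothing about an individual.

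These points make the size of the gap uncertain. They do not supply a route for someone who never answers.

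**Conclusion.** The concern holds as a minor participant-safety point, with medium confidence. Followed as written, and on the natural reading of the damaged sentence, the procedure leaves a participant who is only ever left a message without the EAP details that the plan promises.

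The conclusion assumes that the live-call condition covers the number as well as the score, that the message script does not itself carry the number, and that no page outside the visible text supplies it. The number affected cannot be estimated. There is no consequence for power or for the primary analysis.

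**What to change.** Add a fixed closing screen in REDCap, shown to every participant after the questionnaires at baseline, 6 and 12 months, with the EAP contact details. Keep the coordinator's call for severe scores, and keep disclosure of the score to a live call.

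This works under either reading of the damaged sentence. Because everyone sees the same screen, it reveals no score. It also reaches anyone whose score is high in the footnote's sense but below the severe trigger for a call.

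The cost is one screen on a platform already in use, with no extra staff or contacts. The downside is that participants without symptoms see the details too, and some participants receive them twice. The screen comes after the answers at each wave and is the same in all four conditions. At baseline it also precedes the counseling randomization: "Upon completion of five enrollment measurements (questionnaires, height/weight, waist, ASA24, and blood draw) participants will be randomly assigned".
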